7.3 Time Period and Frequency for Event Assessment and Follow-Up

Adverse events with an onset before the first dose of open-label trofinetide in the present study will be recorded as an AE in the antecedent study. All ongoing AEs from the antecedent trofinetide study will be carried over after informed consent has been obtained for the present study and recorded from Baseline for the present study until resolution or the follow-up safety assessment. An adverse event occurring after the first dose of open-label trofinetide in the present study will be recorded as an AE in the present study. Adverse events for the present study will be recorded from the time of first dose of open-label trofinetide in the present study through the safety follow-up period.

All AEs must be either resolved or stable at the end of the safety follow-up period. If an AE is ongoing at the end of the study safety follow-up period, every reasonable attempt should be made to follow and appropriately treat the subject until the AE resolves or until the Investigator deems the AE to be chronic or stable.

In the event that a subject discontinues and has an ongoing AE at the time of discontinuation ([Section 4.4.2](#)) or is withdrawn from the study because of an AE, the subject should be followed and appropriately treated until the AE resolves or until the Investigator deems the AE to be chronic or stable.

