7.4.2 Serious Adverse Event Reporting

The reporting of SAEs by the Sponsor or designee to the regulatory authorities is a regulatory requirement. Each regulatory authority has established a timetable for reporting SAEs based upon established criteria.

Serious AEs must be reported within 24 hours of discovery to the Sponsor or its designee; use the appropriate form for initial and/or follow-up reporting.

At a minimum, events identified by the Sponsor to require expedited reporting as serious, unexpected, and related to study drug must be brought to the attention of the responsible institutional review board/ethics committee (IRB/EC), as per applicable regulations. These will be provided by the Sponsor after their assessment. For European Union member states, the Sponsor or its designee will provide reports of suspected unexpected serious adverse reactions (SUSARs) directly to the ECs, as required by local legislation. In all other countries, it is the Investigator’s responsibility to provide these expedited reports to the responsible IRB/EC. It is also the Investigator’s responsibility to notify the responsible IRB/EC regarding any new and significant safety information.

When an SAE occurs, Investigators will review all documentation related to the event and will complete the paper SAE form with all required information (for initial and/or follow-up

information) and fax or email (within 24 hours of discovery) to the contact information provided on the SAE form.

Subjects will be followed through the safety follow-up period (i.e., 30 [+4] days after last dose of study drug) for any SAEs and/or other reportable information until such events have resolved or the Investigator deems them to be chronic or stable.

In the event of any SAE (other than death), the study subject will be instructed to contact the Investigator (or designee) using the telephone number provided in the informed consent form (ICF). All subjects experiencing an SAE will be seen by the Investigator or designee as soon as is feasible following the report of the SAE.

Serious AEs occurring after the study follow-up period (i.e., 30 [+4] days after last dose of study drug) should be reported if in the judgment of the Investigator there is “a reasonable possibility” that the event may have been caused by the product.

SAEs should also be reported to the IRB/EC according to local regulations.

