9.5.2 Primary Analyses

Adverse events will be classified into standard terminology using the Medical Dictionary for Regulatory Activities (MedDRA). All AEs will be listed and TEAEs will be summarized by system organ class and preferred term. A TEAE is defined as an AE that started after the first administration of study drug and no later than the last administration of study drug plus 30 days. Summaries by maximum severity and by relationship to study drug will also be provided. Serious TEAEs, fatal AEs, and TEAEs leading to discontinuation will also be summarized.

Descriptive summary statistics for ECG, vital signs and body weight, and clinical laboratory parameters, including observed values and changes from Baseline, will be tabulated by timepoint. Additionally, categorical analyses will be conducted on the incidence of subjects with prolonged QTc intervals and changes in QTc intervals in accordance with International Council for Harmonisation (ICH) guidelines.

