### **14.2 Adverse Events**

Adverse events will be coded using MedDRA dictionary, Version 23.0 or newer.

An AE (classified by preferred term) will be considered a treatment-emergent AE (TEAE) if started after first dose administration and no later than last dose date + 30 days.

The event counts, the number, and percentage of subjects reporting TEAEs in the treatment group of the antecedent DB study and overall will be tabulated by system organ class (SOC) and preferred term; by SOC, preferred term, and maximum severity; and by SOC, preferred term, and relationship to study drug. If more than one TEAE occurs with the same preferred term for the same subject, then the subject will be counted only once for that preferred term using the most severe and most related occurrence for the summarization by severity and by relationship to study drug. The display in these tables will be sorted alphabetically by SOC and then by descending subject frequency for the preferred terms (combined counts from overall group) within each SOC.

The event counts, the number and percentage of subjects with any TEAEs will also be tabulated by preferred term without SOCs. This table will be sorted by descending subject frequency.

The incidence of most frequently reported (preferred terms reported by  $\geq 5\%$  of subjects overall) TEAEs, SAEs reported after treatment start, TEAEs leading to drug withdrawn, and TEAEs related to study drug will be summarized by SOC and preferred term. The tables will be sorted alphabetically by SOC and then by descending frequency within each SOC in overall group. In

addition, the incidence of fatal treatment-emergent AEs (i.e., events that cause death) will be summarized separately by SOC and preferred term.

These summary tables except for the most frequently reported TEAEs tables will also be presented by relationship to COVID-19 related Infection (Not related to COVID-19 Infection vs. Related to COVID-19 Infection).

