An AE listing by subject will display all events, including those which are not treatment-emergent, and will include the verbatim term in addition to the MedDRA SOC and preferred term. This listing will also include all relevant eCRF data associated with the event: date of onset, date resolved, date of last dose, severity, frequency, outcome, relationship to study drug, and action taken with study drug. Separate listings will be presented for treatment-emergent SAEs, related TEAEs, TEAEs leading to drug withdrawn, fatal TEAEs (if any), and TEAEs Related to COVID-19 Infection.

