## **18. CHANGES TO ANALYSES SPECIFIED IN PROTOCOL**

No changes are made to the analyses specified in the protocol.

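### The SAE incidence table in SAP 14.2 has no onset window, so it can count SAEs outside the protocol's serious TEAEs and outside the SAP's own SAE listing (minor)

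*SAP*

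**What the plan says.** SAEs are one of the four primary endpoints (Protocol 2.1.1, SAP 14.1).

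- **Protocol 9.5.2, summary:** "Serious TEAEs, fatal AEs, and TEAEs leading to discontinuation will also be summarized".
- **Protocol 9.5.2, window:** "A TEAE is defined as an AE that started after the first administration of study drug and no later than the last administration of study" (the sentence goes on to allow a further 30 days).
- **SAP 14.2, window:** the same rule. An AE is treatment-emergent "if started after first dose administration and no later than last dose date + 30 days".
- **SAP 14.2, tables:** "SAEs reported after treatment start, TEAEs leading to drug withdrawn, and TEAEs related to study drug will be summarized by SOC and preferred term". The other items in that sentence are TEAEs, and the fatal events in the next sentence are treatment-emergent. Only the SAE item departs from the window.
- **SAP 14.2, listings:** "Separate listings will be presented for treatment-emergent SAEs". A further listing covers all AEs, treatment-emergent or not.
- **SAP 18:** "No changes are made to the analyses specified in the protocol".

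Two protocol sections govern which events outside the window can be recorded. Protocol 7.3 records AEs through the safety follow-up period, and the contact in Protocol 3.1.2 may take place at 30 (+4) days. For later events Protocol 7.4.2 says that "Serious AEs occurring after the study follow-up period (i.e., 30 [+4] days after last dose of study drug) should be reported", on condition that the investigator sees a reasonable possibility that the product caused them.

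**The concern.** Protocol and SAP give two rules for the same primary safety endpoint, and SAP 14.2 itself uses one rule for the SAE table and another for the SAE listing. With no change declared, a programmer cannot tell which is intended, and two programmers could defensibly produce different SAE counts.

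Three things are at stake. The SAE row need not be a subset of the TEAE total. The SAE table need not agree with its own listing. And the table can mix two kinds of data: all-cause SAEs up to the end of follow-up, and after that only SAEs judged possibly related. A single incidence over both has no clear interpretation. The study tests no hypothesis, so descriptive safety incidences are its main product and their definitions should be exact.

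**Working it through.** This is a comparison of definitions. The plan states no figure that depends on it. The one planning number needed is the sample size in Protocol 9.3 and SAP 3.4, which reproduces: 180 × 0.85 = 153.

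**Rules compared**

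1. Serious TEAE (Protocol 9.5.2, and the SAP 14.2 listing): onset after first dose and no later than last dose + 30 days.
2. SAP 14.2 table, literal: report date after treatment start, no upper limit.
3. SAP 14.2 table, loose: onset after treatment start, no upper limit.

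**Hypothetical SAEs.** Last dose is assumed on Day 911, the Week 130 target in SAP Table 2, so the TEAE limit is 911 + 30 = Day 941. These records are illustrative; the documents contain no SAE counts for this study.

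| SAE | Onset day | Report day | Rule 1 | Rule 2 | Rule 3 |
|---|---|---|---|---|---|
| On treatment | 200 | 201 | yes | yes | yes |
| Onset before first dose, found after it | −3 | 2 | no | yes | no |
| Onset and report before first dose, carried over | −20 | −19 | no | no | no |
| Last dose + 30 | 941 | 942 | yes | yes | yes |
| Last dose + 31 | 942 | 943 | no | yes | yes |
| Last dose + 34 | 945 | 945 | no | yes | yes |
| Last dose + 60, judged related | 971 | 972 | no | yes, if in the database | yes, if in the database |
| **Total** | | | **2** | **6** | **5** |

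Every event that meets rule 1 also meets rules 2 and 3, so the SAP table is a superset on either reading. The literal reading adds 6 − 2 = 4 of the seven records and the loose reading adds 5 − 2 = 3. The three late records are extra on both.

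**Can the extra events be recorded?**

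- *Days 31 to 34 after last dose:* yes. The follow-up period runs to 30 (+4) days and AEs of any cause are recorded through it, while the TEAE limit stops at 30. The contact is planned only for subjects who discontinue early or do not start commercial trofinetide within 30 days of completing, so the gap applies mainly to them.
- *After follow-up:* possibly. Protocol 7.4.2 requests these SAEs only if possibly related, with no end date, and describes a paper SAE form. Protocol 7.4.1 sends all AEs to the eCRF. The documents do not say whether an SAE reported after follow-up enters the analysis database.
- *Before first dose:* only under rule 2, and narrowly (see the objection).

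**Size per event.** One extra subject adds 1/153 = 0.0065, or 0.65 percentage points, to the overall SAE incidence. SAP 14 also splits safety tables by treatment group of the antecedent double-blind study. The step is larger there, but the group sizes are not given.

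**The case against.** **The wider table may be intended, and it hides nothing.** The primary endpoint is SAEs without a treatment-emergent limit, the table includes every serious TEAE, and any error is towards counting more harm. This stands as a defence of a wider table. It does not explain why the SAP sets no limits for it, restricts its own listing to treatment-emergent SAEs and declares no change.

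**The word *reported* probably does not mean report date.** SAP 14.2 elsewhere uses *reporting* and *reported* for subjects having an event, and names no report date among its listing fields. This largely stands. A reader might infer that the table is driven by report date, so that SAEs from before first dose enter it and are counted in both studies. The documents do not support that as a general effect. Protocol 7.3 says "Adverse events with an onset before the first dose of open-label trofinetide in the present study will be recorded as an AE" of the antecedent study. AEs are assessed at Baseline, SAEs must be reported within 24 hours of discovery, and a carried-over SAE already reported was not reported after treatment start. The case needs an SAE that begins around rollover and is found only after first dose. Double counting would also depend on the antecedent study's analysis plan, which is not available.

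**Collection is bounded.** Ordinary AE recording stops with follow-up. This stands and narrows the all-cause gap to days 31 to 34; the related-only tail depends on database entry.

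**No event disappears.** The all-AE listing shows every recorded event with onset and last-dose dates. This stands. However, seriousness is not among the fields named for that listing, so reconciling the SAE table from it is not straightforward.

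**Conclusion.** The mismatch is real and minor. The SAE table in SAP 14.2 uses a wider, unbounded definition than Protocol 9.5.2 and than the SAP's own SAE listing, and SAP 18 does not record this. The late gap holds whether *reported* means report or onset: all-cause SAEs on days 31 to 34, plus later possibly related SAEs if they are entered in the database.

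The only supported size is 0.65 percentage points per extra subject, assuming the planned 153 subjects. Counts differ only if an SAE falls in the gap.

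Three stronger conclusions that a reader might draw are not supported:

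- *That the SAE incidence will be inflated by a material relative amount.* This needs the number of true and extra cases, and neither is given. The Phase 2 SAE counts in Protocol 1.3 do not supply them: those studies lasted weeks and included placebo subjects, against up to about 32 months here.
- *That the wide definition is what lets in events on commercial trofinetide.* A subject may start commercial drug within 30 days of completing, so such events can also fall inside the TEAE window. The two definitions do not differ in kind on this.
- *That unrelated SAEs after follow-up show a discrepancy.* They are not requested, so if none is volunteered they are counted under no rule.

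**What to change.** In SAP 14.2, define the SAE incidence table as treatment-emergent SAEs, using the TEAE onset window already given in that section and in Protocol 9.5.2. Show any other recorded SAE, whether carried over from ACP-2566-004 or with onset more than 30 days after last dose, on a separate line outside that incidence. Add a seriousness flag and a treatment-emergent flag to the listing, so that table and listing reconcile event by event.

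If an all-SAE table is wanted, state its start and end by onset date, align the SAE listing with it, and record the change from the protocol in SAP 18.

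The cost is a few words, one table line and two flags, with no new data. The small downside is that the headline SAE incidence may be slightly lower than under the wider wording, with the excluded events shown beside it.

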### **5.8       Missing or incomplete Date for Adverse Events**

Missing or incomplete adverse event (AE) start dates will be imputed for the purpose of determining whether the AEs are treatment-emergent or not (see [Section 14.2](#) for definition). When the chronological order of an AE onset relative to the study drug treatment period is unclear due to missing or incomplete date(s), the AE will be considered as treatment-emergent. The imputation algorithms will be detailed in the analysis dataset specification document. The missing or incomplete dates captured on the eCRF will be displayed in the data listings.

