### **14.1 Primary Safety Endpoints**

The primary safety endpoints are:

- Treatment-emergent adverse events (TEAEs)
- Serious adverse events (SAEs)
- Withdrawals due to adverse events (AEs)
- Potentially clinically important changes in other safety assessments

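### Minor: the table and listing of adverse events leading to drug withdrawal cover only events that began after the first dose in this study, so a carried-over event that ends treatment is left out of both

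*SAP*

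**What the plan says.** SAP 14.1 and Protocol 2.1.1 name four primary safety endpoints. The first is worded as treatment-emergent events. The third is "Withdrawals due to adverse events (AEs"), with no onset condition.

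SAP 14.2 calls an event treatment-emergent "if started after first dose administration and no later than last dose date + 30 days". Protocol 9.5.2 gives the same window. For withdrawals, SAP 14.2 plans this summary: "TEAEs leading to drug withdrawn, and TEAEs related to study drug will be summarized by SOC and preferred term". The dedicated listings follow the same rule: "Separate listings will be presented for treatment-emergent SAEs, related TEAEs, TEAEs leading to drug withdrawn, fatal TEAEs (if any"). Protocol 9.5.2 also limits its discontinuation summary to treatment-emergent events.

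Protocol 7.3 assigns events with onset before the first dose here to the antecedent study. It also carries those still ongoing into this study's records, from Baseline until they resolve or the safety follow-up assessment takes place.

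Two outputs have no onset limit. SAP 14.2 states: "An AE listing by subject will display all events, including those which are not treatment-emergent", and that listing includes the action taken with study drug. SAP 6 tabulates early discontinuations by reason, and Protocol 4.4 includes adverse event among the reasons.

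On deaths, Protocol 9.5.2 plans a summary of fatal adverse events without the treatment-emergent qualifier. SAP 14.2 says "the incidence of fatal treatment-emergent AEs (i.e., events that cause death) will be summarized separately". SAP 18 declares no changes from the protocol's analyses.

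**The concern.** The primary objective is the safety and tolerability of continued long-term treatment. Subjects enter after completing the 40-week open-label study ACP-2566-004, so an onset before the first dose in this study does not mean an onset before exposure to trofinetide. An event that began on drug in the antecedent study, persisted, and finally led to stopping is relevant to that objective. Under the stated rules it is absent from the only table that shows, by system organ class and preferred term, which events ended treatment. It is also absent from the only listing devoted to such events. A reader using those two displays could miss it and would have to find it in the listing of all adverse events.

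**Working it through.** No hypothesis test or power figure is involved. The check compares the definitions and then sizes one affected subject.

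1. **Endpoint.** The same list uses the treatment-emergent term for its first item and the general term for withdrawals (SAP 14.1, Protocol 2.1.1). As worded, the withdrawal endpoint includes events of any onset.

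2. **Display.** The table and listing in SAP 14.2 require onset after the first dose in this study and no later than 30 days after the last.

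3. **Difference.** Protocol 7.3 brings ongoing events from ACP-2566-004 into this study's data with their earlier onset. If one leads to stopping drug and keeps that onset, it meets step 1 and fails step 2. Seriousness plays no part in either step, so serious and non-serious events are treated alike.

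4. **What narrows the gap.**
   - Protocol 7.2.3 gives a new start date to a significant sustained worsening, so an event that worsens in that way after the first dose can qualify as treatment-emergent.
   - Where the order of onset and dosing is unclear because a date is missing or incomplete, SAP 5.8 applies: "the AE will be considered as treatment-emergent". This does not help when onset is known to precede the first dose.
   - At entry, the investigator must judge that the subject may benefit from continuing (Protocol 4.1, criterion 3). Subjects can also be excluded for adverse events in the antecedent study (Protocol 4.2, criterion 5).
   - What remains is an event with known earlier onset, ongoing at entry, never significantly and lastingly worse, that nevertheless ends treatment. An example is a persistent event of unchanged severity that is no longer tolerated.

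5. **Where such an event still shows.** It is in the listing of all adverse events, with the action taken. The subject is in the disposition table under adverse event if that reason was recorded. Protocol 4.4 also offers QTcF increase, physician decision and other reasons, so this is not guaranteed, and disposition gives no system organ class or preferred term. A serious event may also fall under "SAEs reported after treatment start", but that table is not a display of withdrawals.

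6. **Size per subject.**
   - Planned number: 180 × 0.85 = 153 (Protocol 9.3, SAP 3.4), which reproduces the plan's figure.
   - One affected subject in the overall column: 1/153 = 0.0065, or 0.65 percentage points.
   - SAP 14.2 also reports by treatment group of the antecedent double-blind study. Those group sizes are not given, so the corresponding figure there cannot be computed; it would be larger because each group is smaller than the total.
   - The documents give no count of carried-over events that lead to withdrawal, so no total can be derived.

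7. **Fatal events.** Relative to the protocol's wording, the SAP's omits fatal events with onset before the first dose or more than 30 days after the last.
   - Before the first dose: progression to death would normally involve a significant sustained worsening, and so a new start date under Protocol 7.2.3.
   - After the window: follow-up runs to 30 (+4) days after the last dose, so up to four days lie beyond it, plus later serious events judged possibly caused by the product (Protocol 7.4.2).
   - A fatal event is serious by definition (Protocol 7.1.2), so one reported after treatment start belongs in the SAE table by system organ class and preferred term.

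**The case against.** The strongest reply is that the withdrawal displays do what Protocol 9.5.2 specifies, and that the endpoint is in essence a count of subjects, which disposition supplies without an onset limit. The table by preferred term is then a breakdown of the endpoint and not its only summary, and the listing of all adverse events covers the remainder. Much of this stands. There is no departure from the protocol on withdrawals, and the affected group is narrow. What does not follow is that the gap is closed. Disposition depends on the reason recorded and does not identify the event, and a full listing is not a summary. Using the same limit in both documents does not align it with the wider endpoint wording.

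A second reply is that Protocol 7.3 assigns earlier-onset events to the antecedent study, so tabulating them here could blur the two studies. That is a fair caution about presentation, and flagging carried-over events meets it.

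A reader might infer more than the documents support: that these withdrawals go unreported, that the withdrawal rate is materially understated, or that deaths could be hidden. The event remains in the full listing, and the subject is in disposition when adverse event is the recorded reason. No number of affected subjects can be derived. Fatal events reported after treatment start fall in the SAE table.

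**Conclusion.** The point holds as a minor one. The breakdown and dedicated listing for a primary safety endpoint leave out any carried-over event, serious or not, that ends treatment without a new start date, although such an event may have begun on trofinetide. This is a mismatch with the endpoint wording and not a SAP deviation, since Protocol 9.5.2 has the same limit. The number affected may be zero; each one lowers the overall percentage in that table by 0.65 points at the planned 153 subjects. The conclusion assumes that carried-over events keep their original onset date unless Protocol 7.2.3 gives a new one, and that the treatment-emergent rule is applied as written.

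The fatal-event difference between Protocol 9.5.2 and SAP 14.2 is secondary: a wording difference that SAP 18 does not record, with little practical effect.

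**What to change.** In SAP 14.2, tabulate by system organ class and preferred term, and list, all adverse events with drug withdrawn as the action in this study, regardless of onset. Flag those carried over from ACP-2566-004 so that they are not mistaken for new events, and keep the treatment-emergent subset as a separate display.

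For deaths, either summarize all fatal adverse events, as Protocol 9.5.2 words it, or record the restriction to treatment-emergent ones in SAP 18.

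The cost is SAP wording and a few extra outputs. Action taken and outcome are already recorded (Protocol 7.2.5 and 7.2.7), so no new data are needed. The reported AE-withdrawal rate may come out slightly higher.
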